9.6 Potential burdens

The potential burdens to mothers include a) decreased space to move freely in the bed if allocated to the First Days Pēpi-Pod, and b) time taken to consent to participate in the study and complete the questionnaires. This is supported by the New Zealand trial of The First Days Pēpi-Pod, in which two mothers reported that the ‘hospital bed is small’, ‘difficult to use (FDP) for large women’ and that there is ‘not enough room in the hospital bed to get comfortable overnight’ (Cowan 2016).

There is no anticipated burden for infants who participate in this study. Staff who participate will have the burden of completing a survey before and after the pilot that will take approximately 15-20 minutes to complete. All staff on the unit who care for women and babies in the study will participate in the safety briefings associated with use of the safe sleep enablers, similar to staff briefings that are undertaken with the introduction of new hospital equipment.

9.7 Benefits to mother and baby participants

A mother's ease of access to her baby may increase oxytocin levels by promoting maternal-infant gaze and skin-to-skin contact (SSC) (Kim et al, 2014; Moore et al, 2012). In a Cochrane Review conducted by Moore et al (2012), it was found that infants separated from the mother's bedside were 10 times more likely to distress cry than those infants who had SSC with their mother. Babies who are in close contact with their mother have better rates of breastfeeding and thermoregulation than those separated from their mother (Moore et al, 2012). Maternal increase in oxytocin levels, from SSC with the infant, decreases maternal anxiety and risk of post-partum haemorrhage, and increases rates of maternal-infant responsiveness (Moore et al, 2012).

Shared sleeping with an infant by a parent who smokes, or who has taken medications or other drugs which may affect their level of consciousness, significantly increase the risk of sudden unexpected infant death if they sleep with a baby. Shared sleeping in the immediate postnatal environment may occur intentionally as part of the parent's preferred infant care approach or cultural practice in keeping their newborn in close contact; or unintentionally when the mother may fall asleep holding or feeding baby, or during skin to skin contact, particularly in the first 24 hours as advocated in the BFHI guidelines to support successful breastfeeding. Use of a portable safe sleep enabler that is easily accessible to an often less mobile postnatal mother, which facilitates close contact while on a separate sleep surface, has the potential to reduce the risk of a fatal sleeping accident for babies associated with some bed-sharing environments, particularly for mothers who have identified risks (UNICEF, 2012).

Cowan (2016) reported that 86% of mothers would recommend the First Days Pēpi-Pod. The neonatal safe sleep device facilitates more choice with postnatal care, facilitates rooming in (Mitchell et al, 2016), and can be beneficial for mothers who have had a caesarean section (Tully & Ball, 2012). In a mixed-methods study, mothers have variously described the First Days Pēpi-Pod as useful with unsettled babies, beneficial in facilitating ease of access and valuable in promoting independence to care for their baby (Cowan, 2016).

To date, there are no published studies available relating to use and outcomes associated with the MaBim Neonatal Cot.

There are no anticipated direct benefits for staff who choose to participate in this study. If mothers find that ISSD cots keep their baby more accessible to them, this may reduce staff time in responding to call bells to assist mothers to access their babies, particularly for women who have experienced a caesarean section. The impact of new processes and service delivery strategies upon staff work practices is often a factor which influences the success of models of care. Understanding staff perceptions and experiences with the new cots, and how these may influence care and workload, if at all, will provide important information to inform the translation of new models of care into practice to ensure safe and effective outcomes for families.

10. STUDY OUTCOMES

10.1 Primary Outcomes

- Data relating to acceptability of the safe sleep enabler/ISSD by mothers
- Feasibility data - for providing cots; educating staff; ease of implementation for protocol processes: consent, randomisation, safety briefing of parents in context of busy ward environment; documentation.

10.2 Secondary Outcomes

- Maternal satisfaction with care
- Provision of culturally appropriate care
- Accessibility of personal options and choice in care
- Improving breastfeeding rates
- Improving opportunities for maternal-infant attachment
- Improving uptake of safe sleeping recommendations as parents' transition to home environments
- Length of stay
- Safety Data – PRIMES, baby falls, any adverse events that are reported
- Reducing adverse events associated with baby falls from maternal beds or chairs
- Improving staff awareness of safe sleeping recommendations
- Implementation of safe sleep recommendations in the postnatal unit
- Staff satisfaction with postnatal safe sleep enablers
- Data relating to staff perceptions of intervention's impact on workload, e.g. time spent responding to mothers' needs

11. STUDY PROCEDURES

11.1 Recruitment and consent of maternal participants

During the routine 36 week gestation midwife visit, all eligible women will be informed about the study by the midwife by viewing the Information Video and written Participant Information.

After the woman has had time to review the Participant Information Sheet and Consent Form (PISCF), the midwife will obtain written informed consent for her to participate in the study.

A copy of the signed consent is to be given to the participant and Research Assistant, and the original is to be filed in the client health record.

The Study Label is to be placed in the client health record and participant details will be written in the study log book for the Research Assistant to monitor and await the birth.

The total period of recruitment is expected to be four to six months.

11.2 Withdrawal of participants from a study

Participants are free to withdraw from the trial at any time by notifying the treating midwife or research team verbally or in writing. The contact details for the research team will be located on the PISCF. The decision to withdraw from the study will be documented by the

clinician or researcher in the client health record and the Study Log Book which is to be located in clinical areas (Antenatal Clinic and the Postnatal Ward).

11.2.1 Participant withdrawal from study procedures

A participant who withdraws from the study procedure after the birth, though has consented to the study will still have their data collected and analysed up to the point of withdrawal. This is detailed in the PISCF.

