11.4 Measurement tools used

Data collection tools developed for this study have been based on previously used tools, including those recommended in the literature, including:

- ICHOM Pregnancy and Childbirth standard set (ICHOM, 2016) which includes questions relating to breastfeeding outcomes, maternal-infant attachment and maternal satisfaction (Dennis, 2003, Taylor et al., 2005);
- New Zealand First Days Pod evaluation tool (Cowan, 2016);
- Queensland Indigenous Pēpi-Pod® Program evaluations (Young, 2016; Young et al., 2016);
- Published breastfeeding evaluation tools, Breastfeeding Self-Efficacy Scale-Short Form (BSES-SF) (Dennis, 2003) and the Breastfeeding success variable (ICHOM, 2016);
- Queensland Nursing and Midwifery Knowledge, Attitudes and Practices relating to risk for SUDI (Young and Schluter, 2002; Young and O'Rourke, 2003; Young et al., 2008);
- Safe Sleep Education Project Survey and Practice Audit Tools (Young et al., 2010);
- Queensland Infant Care Practice Study (Schluter and Young, 2002; Young et al 2008).

Additional questions have been developed to address specific outcomes of this pilot where no pre-existing tool was available. Please see Table 1 for the outcomes that will be measured.

Table 1: Proposed outcome, measurement tool and time point of data collection

Outcome	Measurement tool	Time point	Person responsible
Maternal and neonatal demographic data	Client Health Record	≥ 36 weeks of gestation AND after birth	Research Assistant, Registered Midwife
Breastfeeding Method	Breastfeeding success variable (ICHOM, 2016)	≤ 3 days / prior to discharge (immediate rate) AND 6-8 weeks (medium rate) AND	Research Assistant, Registered Midwife

		4 months (long term rate)	
Breastfeeding self-efficacy	Breastfeeding Self-Efficacy Scale-Short Form (BSES-SF) (Dennis, 2003)	≤ 3 days / prior to discharge (immediate rate) AND 6-8 weeks (medium rate) AND 4 months (long term rate)	Research Assistant, Registered Midwife
Maternal acceptability of the SSD or control	Questionnaire (author developed)	≤ 3 days / prior to discharge	Research Assistant, Registered Midwife
Staff acceptability of the SSD or control	Questionnaire (author developed)	Approx. 16-20 weeks after study commencement	Research Assistant, Registered Midwife
Maternal-infant attachment	Mother-to-Infant Bonding Scale (MIBS) (Taylor et al., 2005, ICHOM, 2016)	≤ 3 days / prior to discharge AND 6-8 weeks AND 4 months	Research Assistant, Registered Midwife

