Once the mother has birthed, she will be randomly allocated on admission to the postnatal unit to the MaBim side-car crib, First Days Pēpi-Pod® or control (usual care with baby sleep space being independent hospital Perspex cot on wheels) during the postnatal stay.

All participants will be shown the Video Clip titled 'Safe, Sleep, Little One' (CFOC Ltd, 2016) by the midwife once orientated to the ward. If allocated to the First Days Pēpi-Pod, participants will also be asked to view the Picture Demonstration (CFOC Ltd, 2016). Participants allocated to the MaBim neonatal crib will be shown the MaBim Product Brochure. Those randomised to the control group (usual cot care) will receive standard care instructions.

Participants will be followed up by the Research Assistant during the hospital admission to assess breastfeeding rates, acceptability of the ISSD or control, maternal-infant attachment, maternal satisfaction with the care received, culturally appropriate care, accessibility of personal options and choice in care, adverse events (baby falls from maternal beds or chairs) and awareness of, and compliance with, safe sleeping recommendations. Participants will be asked to complete the questionnaires, expected to take thirty minutes of the participants' time. The participant will be given the choice to complete the questionnaires independently or have the Research Assistant read the questions. The questionnaire will be available online (Opinio Survey Software 7.1) and in paper format.

If participants discharge prior to contact with the Research Assistant, she will be contacted within seventy-two hours of discharge, or at the next time of convenience.

Prior to discharge, participants will be asked to view the 'Red Nose Safe Sleeping' information (SIDS and Kids Australia, 2016) available via the mobile phone application. This information video promotes safe sleeping practices in the home environment.

Infant sleep observation and maternal chart audits for participating mothers and babies will be conducted (using the audit tools described in Phase 1) prior to discharge.

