12.2 Data analysis

Data collection and analyses will include maternal and infant demographics; breastfeeding outcomes (at discharge, 6-8 weeks and 4 months); length of stay; maternal-infant attachment; maternal satisfaction and perceptions relating to enabler use; staff time to recruit and educate families, perceptions relating to intervention impact and adverse events; and maternal and

staff awareness of safe sleep recommendations (self reported and observed). Data from this pilot, the first Australian trial of a hospital postnatal safe sleep enabler, will be used to inform a randomised controlled trial of safe sleep enablers in postnatal environments.

Maternal Data: Analysis of maternal data will be conducted using the principles of intention to treat. All participants who were enrolled and randomly allocated to treatment are included in the analysis and will be analysed in the groups to which they were randomised. A further analysis will be based on actual use, consistent with a recent published study on Wahakura use, a Maori safe sleep enabler, intended for domestic use after discharge home to the community (Baddock et al., 2017) which performed analyses based on intention to treat and actual use.

Statistical analyses will be performed to report the prevalence and proportions of variables surveyed. Questionnaire results will be entered into a purpose-built Microsoft Excel database for data cleaning and preparation for statistical analysis. A 10% random selection (approximately 9-10 questionnaires from each of the maternal records, staff survey and audits) will be double entered to assess data-entry accuracy and intra-rater reliability. Consistency checks will be performed on all variables to ensure that only valid responses will form the basis of the ensuing analysis.

Quantitative data will be analysed using descriptive techniques such as frequency and percentage and measures of central tendency and distribution (for example, mean and standard deviation or median and IQR). Normality of data will be assessed. Group comparisons to comparing equivalency of control and interventions will be conducted with Chi-squared test for categorical measures and analysis of variance or Kruskal-Wallis test for continuous measures as appropriate assessing for normality and equality of variances.

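### Section 11.2.1 does not separate giving up the allocated cot from leaving data collection, so mothers who reject a device could be lost before primary acceptability is measured

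*Protocol*

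**What the plan says.** Protocol section 11.2 deals with leaving the trial: "Participants are free to withdraw from the trial at any time by notifying the treating midwife or research team verbally or in writing". Section 11.2.1 follows under its own heading, on withdrawal from study procedures, and applies to "A participant who withdraws from the study procedure after the birth, though has consented to the study". Such a mother "will still have their data collected and analysed up to the point of withdrawal". The section refers to the participant information and consent form for the detail.

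The first primary outcome in section 10.1 is "Data relating to acceptability of the safe sleep enabler/ISSD by mothers". In Table 1 (section 11.4), the row for "Maternal acceptability of the SSD or control" has one time point, within 3 days or before discharge. Section 11.5.1 adds a catch-up for mothers who go home before the Research Assistant reaches them: "she will be contacted within seventy-two hours of discharge, or at the next time of convenience". Breastfeeding, attachment and safe sleeping are assessed again at 6-8 weeks and 4 months.

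Section 12.2 sets the analysis population: "All participants who were enrolled and randomly allocated to treatment are included in the analysis", in the groups to which they were randomised. It continues: "A further analysis will be based on actual use". Section 11.3 intends each cot allocation to last for the hospital stay. It has the Project Register record the allocation, any unavailability and any reallocation to a standard cot. Refusal or return by the mother is not among the items listed.

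**The concern.** For a device-arm mother, the most visible study procedure after birth is the allocated cot. A midwife whose participant declines the cot when the envelope is opened, or hands it back on the first night, could reasonably apply 11.2.1 and stop collecting her data. That mother would leave before the only acceptability questionnaire, and her reason for leaving may be that she found the device unacceptable. The primary outcome would then be estimated mainly in mothers content to keep the device.

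Return is foreseeable. Section 9.6 reports users in the New Zealand trial run who found the hospital bed too small with the First Days Pēpi-Pod. Section 9.5 lists discomfort after caesarean section. Every bed has a standard cot to fall back on (section 11.3). Control mothers have no new device to hand back, so losses of this kind would fall mainly in the device arms. Comparisons of satisfaction, attachment and breastfeeding could be affected as well. Data that were never collected cannot be recovered by any later analysis plan.

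**Working it through.** **1. The plan's own figures.** Section 11.3 enrols at least 60 per group (180 in total), allows up to 50% attrition, and aims for 30 per group with complete data. These agree: 30 / (1 − 0.5) = 60 and 90 / (1 − 0.5) = 180. The allowance is tied to the four months after discharge. It does not address loss before the in-hospital acceptability questionnaire.

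**2. The passages side by side.**
- Section 11.2 covers leaving the trial. Section 11.2.1 covers withdrawal from the study procedure by a woman who has consented to the study. The separate heading suggests that something narrower than leaving the trial is meant.
- Section 11.2.1 carries data only to the point of withdrawal.
- Acceptability has one time point. The catch-up contact in 11.5.1 is for early discharge, not for mothers who give up the cot.
- Section 12.2 includes all randomised mothers as randomised. A mother whose data stopped before the questionnaire has no acceptability value to include.
- No section says that data collection continues after a cot is declined or returned, and none says that it stops.

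**3. Size if 11.2.1 is applied to returners.** Let *r* be the share who decline or return the device and so give no acceptability answer, *a_k* the acceptability among keepers, and *a_r* the acceptability among returners.

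- Reported figure = *a_k*
- Figure among all allocated = (1 − *r*) × *a_k* + *r* × *a_r*
- Overstatement = *r* × (*a_k* − *a_r*)

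Inputs: *a_k* = 86%, the share who would recommend the First Days Pēpi-Pod in the earlier trial run (section 9.7). It is used for illustration only and is not a planning assumption of this pilot. The documents give neither *r* nor *a_r*, so both are assumed.

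| Assumed *r* | Mothers out of 60 | All allocated, *a_r* = 0 | Overstatement, *a_r* = 0 | All allocated, *a_r* = 30% | Overstatement, *a_r* = 30% | Overstatement, *a_r* = 86% |
|---|---|---|---|---|---|---|
| 5% | 3 | 81.7% | 4.3 points | 83.2% | 2.8 points | 0 |
| 10% | 6 | 77.4% | 8.6 points | 80.4% | 5.6 points | 0 |
| 20% | 12 | 68.8% | 17.2 points | 74.8% | 11.2 points | 0 |
| 30% | 18 | 60.2% | 25.8 points | 69.2% | 16.8 points | 0 |

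Example: *r* = 20% and *a_r* = 0 gives 0.80 × 0.86 = 0.688, and 0.860 − 0.688 = 0.172.

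**The case against.** The strongest reply is that the protocol never equates returning the cot with withdrawal. Section 11 as a whole is headed Study Procedures and covers consent, randomisation, questionnaires and follow-up, so withdrawing from the study procedure may simply mean ceasing to take part. On that view 11.2.1 only preserves data already collected. Section 11.3 makes cot use an intention for the stay, which leaves room for departures. If stopping use is not withdrawal, the tension with section 12.2 disappears. The consent form to which 11.2.1 refers is not among the documents and may settle the matter. All of this stands, and it makes the concern conditional.

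Three further limits also stand. First, a reader might infer that the actual-use analysis proves that returners must be followed, because use could not otherwise differ from allocation. That does not follow: section 11.3 moves a mother to a standard cot when her allocated device is in use, and expects this for about half of those randomised to MaBim. Second, the loss need not be wholly one-sided, because the study is unblinded and control mothers may also withdraw. Third, the 86% concerns one device and a different question, and section 9.7 says there are no published studies of the MaBim.

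The reply does not show that the text is clear. The ward has two workable readings, and one of them discards the primary outcome for the mothers who are most informative about it.

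**Conclusion.** The point holds as an ambiguity with a potentially serious consequence. Section 11.2.1 fails to separate giving up the cot from ending data collection, and its literal wording could remove mothers before the single acceptability measurement. A reader might go further and conclude that a mother who returns the device is counted as withdrawn, so that acceptability is certain to be overstated. The documents do not support that: no section states it, and the intention to analyse everyone randomised points the other way.

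The overstatement is 0 to about 26 percentage points. This assumes that return stops data collection, that up to 30% return the device, and that 86% of keepers are favourable. The top of the range also needs no returner to be favourable. At zero, returners rate the device as keepers do, which is unlikely when return reflects dissatisfaction. The true size cannot be derived from the documents.

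Clarification is worth making because maternal acceptability and the feasibility of the protocol are both primary outcomes, and because this protocol is meant to inform the larger trial.

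**What to change.** Amend section 11.2.1, and the participant information to match, to distinguish two events:

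- **Stopping or declining the allocated cot.** The mother stays in the study, is offered the acceptability and satisfaction questionnaires when she stops or at discharge, and is followed at 6-8 weeks and 4 months.
- **Withdrawing consent to data collection.** Only this ends collection. Data gathered up to then are kept, as now.

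Add the date and reason of any refusal or return to the Project Register. Report the proportion declining or returning each device beside the acceptability result. Scoring every return as not acceptable is not recommended as the primary rule, since a cot may be returned for reasons unrelated to the device. The change concerns data collection only and leaves the use of the cots as it is.

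The cost is a wording amendment and one extra register entry, with no added participants or visits. The reported acceptability may be less favourable.

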11.3 Randomisation

The aim of this pilot study is to test the concept of a novel cot/safe sleep enabler in the maternity unit in the first instance. The availability of the MaBim Neonatal Cot will be limited to 4 cots (due to costs) and the First Days Pēpi-Pod® will be limited to 15 cots for this pilot. All beds will have a standard cot available.

This study intends to provide information to inform the development of a protocol for a randomised controlled trial. The pilot protocol will include a trial of the randomisation process to be used in the larger trial as staff education relating to processes used in the pilot have been considered. Introducing differences in the randomisation process to accommodate the unequal number of intervention cots was considered problematic; particularly as feasibility of the protocol was a key outcome of the pilot. The following methodology for randomisation has been adopted based on the intentions of the pilot within the resource limitations of limited numbers of First Day the pilot study, and is believed to be workable given the average length of stay of mothers in this maternity unit.

On arrival to the postnatal unit, participants will be randomised to one of three options; ‘The First Days Pēpi-Pod®’, ‘The MaBim Neonatal Cot’ or a standard bedside cot. The midwife will take the next sealed, opaque envelope located on a box of envelopes, in a locked cabinet, in the midwives’ work station. The midwife in charge of the shift will hold the key for the cabinet. Inside the envelope will either be a label stating, ‘The First Days Pēpi-Pod®’, ‘The MaBim Neonatal Cot’ or standard bedside cot. This randomisation label will then be placed on the postnatal pathway. The midwife in charge will make an entry in the Project Register (held in locked cabinet with sealed envelopes) of participant name, envelope number and cot allocation.

If the allocated cot is not available (i.e. the First Days Pepi-Pod® or MaBim are already in use) the participant will be allocated to a standard cot. These allocations will be managed as a fourth group in the analysis in which demographic information should theoretically be similar to the standard cot allocated group. This method also serves as an internal checking procedure for the randomisation process used in the clinical environment. In this instance, the midwife in charge will make an entry in the Project Register for participant name, envelope number, first cot allocation, non-availability and reallocation to standard cot and will place the envelope into the discard box (to allow checking of integrity of the randomisation process).

A total of 300 envelopes will be prepared representing each of the three options equally (100/100/100) and which will also allow for the envelope discard process. A mock run of the randomisation process indicated that based on an estimated 7 deliveries per day and an average stay of 3 days, the four MaBim cots would be in almost constant use and approximately half of those mother-baby pairs randomised to the MaBim would be allocated

to use them. This process will allow integrity of the randomisation of process while still maintaining recruitment for each target sample within a feasible timeframe.

An allocation to a cot is intended for the duration of hospitalisation. The usual length of hospital stay for a woman having a vaginal delivery is 1-3 days; for a woman delivering by caesarean section 3-5 days. Analyses will be by Intention to Treat according to actual allocation and Actual Use, consistent with a recent randomised controlled study of safe sleep enabler use (Baddock et al., 2017).

The study will continue until there is a minimum of 60 participants in each group (total n=180) and will allow an attrition rate of up to 50% during the 4 month follow-up period following discharge from the post-natal unit. The final target sample for this pilot is 30 participants in each group with a complete data set.

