5. HYPOTHESES

5.1 Primary Hypotheses

The priority of the pilot is to test the novel concept of safe sleep enablers for the first time in an Australian setting. Two primary hypotheses will focus on maternal acceptability of the safe sleep enablers as alternative infant sleep spaces and the feasibility of the proposed protocol in a busy maternity setting.

The primary hypotheses are:

1. Acceptability with infant safe sleep enablers will be demonstrated by mothers in the maternity unit setting.
2. Feasibility of a pilot protocol to evaluate safe sleep enablers in the maternity unit setting will be demonstrated (as measured by staff support, appropriate application of the protocol: consent, randomisation, documentation processes).

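### Section 11.3 does not require the mother and envelope number to be recorded before the envelope is opened, so substitution is not prevented in this non-blinded trial

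*Protocol*

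**What the plan says.** Protocol section 11.3 describes the steps on arrival at the postnatal unit:

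- Drawing: "The midwife will take the next sealed, opaque envelope located on a box of envelopes, in a locked cabinet".
- Access: "The midwife in charge of the shift will hold the key for the cabinet".
- Label: "This randomisation label will then be placed on the postnatal pathway".
- Register entry: "The midwife in charge will make an entry in the Project Register (held in locked cabinet with sealed envelopes) of participant name, envelope number". The allocated cot is the third item in that entry.
- Allocated cot already in use: the register instead takes "participant name, envelope number, first cot allocation, non-availability and reallocation to standard cot", and the midwife in charge "will place the envelope into the discard box (to allow checking of integrity of the randomisation process").

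The stock is 300 envelopes, 100 for each of the three options. Section 12.1 calls the trial protocol under test non-blinded. Section 5.1 makes "appropriate application of the protocol: consent, randomisation, documentation processes" part of the second primary hypothesis, and section 10.1 lists ease of randomisation among the primary feasibility data. Section 12.2 analyses the maternal data by randomised group, with a further analysis by actual use.

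**The concern.** Sealed, opaque envelopes used in order stop staff from reading ahead. They do not stop someone from opening an envelope, disliking what it shows, and then deciding which mother receives it. What closes that gap is an irrevocable entry of the mother against the numbered envelope while it is still sealed. Section 11.3 has no such step.

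The protocol itself gives reasons why staff might prefer one cot for one mother. Section 9.5 names discomfort after caesarean section with the pod and with the standard cot, but not with the MaBim. The text on benefits after section 9.7 suggests that more accessible cots may reduce call-bell work, particularly after caesarean section.

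Two things are at stake. If allocations were exchanged before being recorded, the intention-to-treat groups would no longer be random, and no later analysis could repair that. The pilot is also meant to try out the randomisation process for the larger trial, planned at 1,362 mothers in section 12.1. A check that cannot see one kind of failure could report the process as sound when it was not.

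**Working it through.** The plan states no figure on this point, so the check sets the steps side by side.

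**1. When can the register entry be made?** The entry has three items: name, envelope number and cot allocation. The first two are known before opening; the third is not. The entry as a whole can therefore be completed only after opening. Section 11.3 does not ask for the first two items to be written earlier, and lists no date, time or second signature.

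**2. What would the existing trail reveal?**

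| Event | What the records would show |
|---|---|
| Envelope skipped, hidden or destroyed | A missing number against the register and the stock of 300 |
| Opened envelope held for a clearly later mother | Numbers out of step with admission order, if someone compares them with admission dates |
| Two envelopes exchanged between mothers admitted close together | Every number used, arm totals unchanged, each pathway label agreeing with the register |

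For the last row, suppose for illustration that envelope 41 holds a pod label and envelope 42 a MaBim label, with mothers A and B arriving within hours of each other. The procedure should give A–41–pod and B–42–MaBim. After an exchange the records read A–42–MaBim and B–41–pod. Each number still matches its label. With no time recorded, nothing in the register shows that 41 was drawn for A.

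**3. Does the discard box cover this?** It is stated for mothers whose allocated cot is not available. For all others the protocol does not say what happens to the opened envelope.

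**4. How readily would a second draw differ?** Assume a randomly ordered, full stock of 100/100/100, with one envelope opened.

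- Next envelope shows a different arm: 200/299 = 66.9%.
- At least one of the next two does: 1 − (99/299)(98/298) = 89.1%.
- Next envelope shows one particular other arm: 100/299 = 33.4%.
- At least one of the next two shows that arm: 1 − (199/299)(198/298) = 55.8%.

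These figures describe opportunity only. They say nothing about how often staff would act on it, or about the resulting bias.

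**The case against.** The procedure already has real safeguards: opaque numbered envelopes, a next-in-order rule, a locked cabinet, a register, a label on each mother's pathway and a known stock. Roles are partly separated, since one midwife takes the envelope while the midwife in charge holds the key and writes the register. A second draw would need her access or cooperation. Motive should not be overdrawn either. MaBims are expected to be in almost constant use, so steering a mother to one would often gain nothing, and every bed has a standard cot anyway. Section 11.5.2 also provides a staff briefing with written information that covers randomisation. All of this stands, and it limits the concern.

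Three stronger readings are tempting and are not supported:

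- A reader might infer that an allocation can be exchanged without any trace. The trail is partial, not absent: a missing envelope would show, and a long hold-over would disturb the sequence.
- A reader might infer that the protocol prescribes registration last. The word *then* governs only the label step, and the register sentence carries no time word. Writing name and number when the envelope is taken is compatible with the text. It is simply not required.
- A reader might infer that used envelopes are thrown away. The protocol is silent on them.

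The safeguards do not supply a commitment before opening, and they do not reach a close-in-time exchange. That part of the concern remains.

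**Conclusion.** The concern holds in a limited form. Section 11.3 does not require the mother's identity and the envelope number to be recorded before opening, and its only register entry is completed after the allocation is known. Substitution is therefore not prevented, and an exchange between two mothers admitted close together could pass both the register and the discard-box check.

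No size of bias can be given. A reader might want to express it as a spurious difference in length of stay, but that would need a redraw rate and a caesarean share that the documents do not state. It would also need a model that keeps arm totals equal, as an exchange does. The conclusion rests on the wording of section 11.3 and on the assumption that the ward follows it without an unwritten extra step.

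This is a worthwhile tightening of a concealment method rather than the correction of a plain error. It matters more than usual for a pilot because the randomisation process is itself under test.

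**What to change.** In section 11.3, place the commitment before opening:

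1. The midwife writes the mother's study ID, date and time on the next numbered envelope while it is sealed, and the same details go into the Project Register.
2. Only then is the envelope opened. Its allocation stands as the randomised group, including where the existing unavailability route leads to a different cot being used.
3. Every opened envelope is kept, not only those in the discard box.
4. The research team holds the numbered allocation list off the ward. The Research Assistant periodically reconciles number, time and allocation against it.
5. Discrepancies are counted and reported as part of the randomisation feasibility outcome.

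The change uses the existing envelopes, register and Research Assistant. It costs a revision of section 11.3, about a minute per mother, and the time for periodic reconciliation. It changes no rule on which cot a mother uses.
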